9.2.4.2 Pregnancy Testing

[figure not shown]
A high sensitive serum pregnancy test should be completed at screening and a high sensitive urine test should be completed within 7 days of initiation of investigational product for females of childbearing potential. Therefore, for this study, the initial pregnancy tests will occur at screening and at the day 1 visit (which is within 7 days of initiation of investigational product).

Note: Females who have undergone a bilateral tubal ligation/occlusion should have pregnancy testing per protocol requirements. (If a female subject, or the partner of a male subject, becomes pregnant it must be reported on the Pregnancy Notification Worksheet, see [Figure 12-2](#)). Refer to [Appendix 5](#) for contraceptive requirements.

Additional pregnancy testing should be performed monthly during treatment with protocol-required therapies, then at week 52 and week 70 during the safety follow-up period.

If a urine pregnancy test is positive, a confirmatory serum pregnancy test will be performed and entered into the electronic case report form (eCRF).

[figure not shown]
Additional on-treatment pregnancy testing may be performed at the investigator's discretion or as required per local laws and regulations.

9.2.5 Pharmacokinetic Assessments

All subjects randomized to treatment with tezepelumab will have pharmacokinetic samples assessed.

Whole blood samples of approximately 5 mL will be collected for measurement of serum concentrations of tezepelumab as specified in the Schedule of Activities ([Table 2-1](#) and [Table 2-2](#)). A maximum of 2 samples may be collected at additional time points during the study if warranted and agreed upon between the investigator and the sponsor. Instructions for the collection and handling of biological samples will be provided by the sponsor. The actual date and time (24-hour clock time) of each sample will be recorded. Drug concentration information that may unblind the study will not be reported to investigative study centers or blinded personnel until the study has been unblinded.

9.2.7 Pharmacogenetic Assessments

If the subject consents to the optional pharmacogenetic portion of this study, DNA analyses may be performed. These optional pharmacogenetic analyses focus on inherited genetic variations to evaluate their possible correlation to the disease and/or responsiveness to the therapies used in this study. The goals of the optional studies include the use of genetic markers to help in the investigation of moderate-to-severe AD and/or to identify subjects who may have positive or negative response to investigational product or protocol-required therapies. Samples collected for this part of the study are described in [Section 9.2.9.3](#). For subjects who consent to this/these analysis/analyses, DNA may be extracted. The final disposition of samples is described in [Appendix 6](#).

9.2.8 Antibody Testing Procedures

Blood sample(s) for antibody testing are to be collected according to the time points specified in the Schedule of Activities ([Table 2-1](#) and [Table 2-2](#)). Bioanalytical testing for anti-tezepelumab antibodies will be conducted only if there are unexpected PK findings or safety-related concerns in the study population that warrant further investigation. Samples that test positive for anti-tezepelumab antibodies may be further characterized. Additional blood samples may be obtained to rule out the presence of anti-tezepelumab antibodies during the study.

Refer to the laboratory manual for detailed collection and handling instructions.

9.2.9 Biomarker Development

Biomarkers are objectively measured and evaluated indicators of normal biologic processes, pathogenic processes, or pharmacologic responses to a therapeutic intervention.

Biomarker development can be useful in developing markers to identify disease subtypes, guide therapy, and/or predict disease severity.

Amgen may attempt to develop test(s) designed to identify subjects most likely to respond positively or negatively to tezepelumab to investigate and further understand moderate-to-severe AD.

Blood samples and biopsies are to be collected according to the Schedule of Activities ([Table 2-1](#) and [Table 2-2](#)). Refer to the Laboratory Manual for detailed collection and sample handling procedures for biomarker assessment.

9.2.9.1 Blood Biomarkers

Blood samples (serum/plasma and whole blood) will be collected as outlined in [Table 2-1](#) and [Table 2-2](#) for the assessment of changes in circulating biomarker levels that are elevated in subjects with AD. Additional assays which may be performed on blood samples include measuring changes in mRNA transcripts after tezepelumab treatment.

9.2.9.2 Skin RNA Transcript Profiling

Skin punch biopsy samples will be collected from a subset of consenting subjects according to the Schedule of Activities ([Table 2-1](#) and [Table 2-2](#)) for RNA transcript analysis. The purpose of these analyses will be to retrospectively evaluate transcript biomarkers predictive of subject response at baseline, prior to investigational product administration, as well as to potentially identify additional AD biomarkers.

9.2.9.3 DNA

Whole blood will be collected at a single time point (day 1 visit) after subjects have been randomized into the study for extraction of DNA and analysis of polymorphisms associated with AD, TSLP, or tezepelumab response. The collection of blood for DNA analysis is optional and subjects who do not wish to have the DNA test done will still be eligible for the study. The completion of a separate Informed Consent Form (Pharmacogenetic ICF) related to DNA is required. Subjects who elect to have the DNA test done may, at any time before the end of the study, request that the blood collected for DNA analysis be destroyed.

9.2.10 Clinical Outcome Assessments

9.2.10.1 EQ-5D-3L

The EuroQOL quality of life 5-dimensions 3-level version (EQ-5D-3L) is a standardized instrument for use as a measure of health-related quality of life (HRQoL) and was developed by EuroQol ([Brooks, 1996](#)). It defines health in terms of 5 dimensions: mobility, self-care, usual activities, pain/discomfort, and anxiety/depression. Each dimension has 3 ordinal levels of severity: 1, no problem; 2, some problems; and 3, severe problems. Overall health state is defined as a 5-digit number. The EQ-5D-3L will be assessed at the study center, according to the Schedule of Activities ([Table 2-1](#) and [Table 2-2](#)).

9.2.11 Optional Substudies

Optional substudies include skin punch biopsies (biomarker) and the sample for DNA analysis (pharmacogenetics). Obtain confirmation that the optional substudy ICF has been signed prior to performing any optional substudy procedures.

9.2.12 Other Assessments

Not applicable to this study.

10. Statistical Considerations

10.1 Sample Size Determination

In Part A of this study, a total of 240 subjects will be randomized in a 1:1:1:1 ratio to tezepelumab 420 mg SC Q2W, 280 mg SC Q2W, 210 mg SC Q4W, and placebo (approximately 60 in each group). There is at least 85% power for each co-primary endpoint, assuming IGA 0/1 response rates of 10% and 40% for placebo and the highest tezepelumab dose group (420 mg SC Q2W), respectively, and assuming EASI response rates of 15% and 50%, respectively. These assumed treatment effects are based on the results of other new agents in this indication ([DUPIXENT, 2017](#)). These calculations used a 2-sided χ^2 test at a significance level of 0.025 (to reflect the Bonferonni-based gatekeeping procedure described in [Section 10.3.2.1](#)) and assumed a 10% dropout rate.

Part B of this study is exploratory. A sample size of 60 subjects (40 in the tezepelumab 420 mg SC Q2W group and 20 in the placebo group) was chosen as an adequate sample size to provide initial evidence of tezepelumab as a promising agent for adjunct therapy.

10.2 Analysis Sets, Subgroups, and Covariates

10.2.1 Analysis Sets

Part A and Part B of the study will be analyzed separately, therefore, the analysis sets described below will be created for each study part.

10.2.1.1 Full Analysis Set

The full analysis set will include all randomized subjects. Subjects will be analyzed according to their randomized treatment group. Demographics, baseline disease characteristics, and efficacy analyses will be based on the full analysis set.

10.2.1.2 Safety Analysis Set

The safety analysis set will consist of all randomized subjects who receive at least 1 dose of investigational product. Subjects will be analyzed according to the actual treatment received. The safety analyses described in [Section 10.3.2.3](#) will be based on the safety analysis set.

10.2.1.3 PK Analysis Set

Subjects who receive investigational product and have a sufficient number of serum concentration measurements for computing PK parameters will be included in the PK analysis set and subjects will be analyzed according to the treatment they actually receive.

10.2.2 Covariates

The analysis of the primary endpoints will be adjusted for the following baseline covariates:

- Baseline EASI (for EASI 75 at week 16)
- Baseline IGA (for IGA 0/1 at week 16)

Additional covariates may be considered in exploratory analyses and will be described in the Statistical Analysis Plan (SAP).

10.2.3 Subgroups

This study is not powered to draw conclusions from subgroup analyses. However, exploratory subgroup analyses based on the covariates above will be conducted to examine the consistency of the treatment effect for the primary endpoints for Part A. Additional subgroups for Part A will be specified in the SAP. Subgroup analyses are not planned for Part B.

10.2.4 Handling of Missing and Incomplete Data

Subjects missing data for the primary endpoints will be considered non-responders (ie, non-responder imputation). The last observation carried forward and multiple imputation methods may also be considered in sensitivity analyses. Similar methods will apply for the secondary endpoints EASI 50 and EASI 90 response. For the change from baseline to week 16 secondary endpoints, subjects missing week 16 will have their last observation carried forward; multiple imputation and a completers analysis may also be considered in sensitivity analyses.

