7.1.5 Other Treatment Procedures

During the 28-day screening period, subjects must discontinue from all AD therapies, except for approved moisturizers (see [Section 7.1.7](#)), for at least the 7 consecutive days immediately prior to day 1. During the study, approved moisturizers are allowed to be applied, with the exception of 8 hours prior to any scheduled visit.

Medications and procedures permitted at any time during the study for subjects enrolled in Part A and Part B include:

- Basic skin care (cleansing and bathing), emollients, bleach baths, topical anesthetics, and antihistamines (all for any duration)
- Medications used to treat chronic diseases such as diabetes, hypertension, and asthma

Part A

In Part A of the study, if needed to control intolerable AD symptoms, rescue treatment for AD may be provided at the discretion of the investigator. Rescue is not allowed in the first 4 weeks of Part A. Topical calcineurin inhibitors may be used for rescue, but are to be reserved for problem areas only (eg, face, neck, intertriginous and genital areas). Investigators are to attempt to limit the first step of rescue therapy to topical medications, and escalate to systemic medications only for subjects who do not respond adequately following at least 7 days of topical treatment. If a subject receives rescue treatment with systemic corticosteroids or nonsteroidal systemic immunosuppressive drugs

(eg, cyclosporine, mycophenolate-mofetil, azathioprine), study treatment is to be immediately discontinued.

All subjects are to complete the schedule of study visits and assessments whether or not they complete study treatment or receive rescue treatment for AD.

Part A Rescue Guidance

Subjects who use TCS are to apply medium potency TCS once daily to areas with active lesions. Low potency TCS should be used once daily on areas of thin skin (eg, face, neck, intertriginous, genital areas, areas of skin atrophy) or for areas where continued treatment with medium potency TCS is considered unsafe.

Triamcinolone acetonide 0.1% cream or fluocinolone acetonide 0.025% ointment are recommended as medium potency TCS therapy; hydrocortisone 1% cream is recommended as low potency TCS therapy. After lesions are under control (clear or almost clear), subjects are to switch from medium potency to low potency TCS and treat once daily for 7 days, then cease TCS therapy.

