## 2. Objectives, Endpoints and Hypotheses

### 2.1 Objectives and Endpoints

Objectives	Endpoints
Primary – Part A	

To evaluate the effect of tezepelumab compared with placebo, assessed using the Investigator's Global Assessment (IGA) and Eczema Area and Severity Index (EASI)

	

IGA score of 0 (clear) or 1 (almost clear) (IGA 0/1) at week 16

75% reduction in EASI (EASI 75) at week 16

The first primary estimand consists of:

- Target population – patients with moderate-to-severe atopic dermatitis (**AD**).
- Endpoint – IGA 0/1 at week 16.
- Intercurrent event – there are 2 intercurrent events, discontinuation of IP before week 16 and **concurrent use** of rescue medication **with TCS/TCI** between day **29** and week 16. Treatment effects will be estimated for subjects regardless of whether patients complete 16 weeks of **study treatment**. The use of rescue medication is captured through the endpoint definition in **Section 5.5, and use of TCS/TCI will be classed as a non-response**.
- Summary measure – odds ratio comparing the odds of achieving endpoint on tezepelumab 420 mg Q2W compared to the odds of achieving endpoint on placebo.

In summary, the first primary estimand is the odds ratio between tezepelumab 420 mg Q2W and placebo in achieving IGA 0/1 at week 16, in the absence of rescue medication with **TCS/TCI regardless of whether patients complete 16 weeks of study treatment**, in patients with moderate-to-severe AD.

The second primary estimand is the odds ratio between tezepelumab 280 mg Q2W and placebo in achieving IGA 0/1 at week 16, in the absence of rescue medication with **TCS/TCI regardless of whether patients complete 16 weeks of study treatment**, in patients with moderate-to-severe AD.

The third primary estimand is the odds ratio between tezepelumab 420 mg Q2W and placebo in achieving EASI 75 at week 16, in the absence of rescue medication with **TCS/TCI regardless of whether patients complete 16 weeks of study treatment**, in patients with moderate-to-severe AD.

The fourth primary estimand is the odds ratio between tezepelumab 280 mg Q2W and placebo in achieving EASI 75 at week 16, in the absence of rescue medication with **TCS/TCI regardless of whether patients complete 16 weeks of study treatment**, in patients with moderate-to-severe AD.

Secondary – Part A	

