

To estimate the effect of tezepelumab compared with placebo on the efficacy measure of EASI

	

50% and 90% reduction in EASI (EASI 50/90) at week 16

To estimate the time needed to reach EASI 50/75/90

	

Time at which EASI 50/75/90 is achieved from day 1

To estimate the effect of tezepelumab compared with placebo on the efficacy measure of Scoring Atopic Dermatitis (SCORAD)

	

SCORAD at week 16

To estimate the effect of tezepelumab compared with placebo on the patient-reported outcome (PRO) measure of pruritus assessed using a numeric rating scale (NRS)

	

Pruritus NRS at week 16

To characterize the pharmacokinetics (PK) of tezepelumab

	

Serum trough concentrations of tezepelumab at scheduled visits

The secondary estimands are described in the same way as primary estimands except the endpoint attribute will change for EASI 50/90 at week 16, SCORAD at week 16 and Pruritus NRS at week 16, where the summary measure changes to be the Least Square Mean difference; and time at which EASI 50/75/90 is achieved from day 1, where the summary measure changes to be the median time to achieve EASI 50/75/90 from day 1.

Safety – Part A and Part B	

 
To establish the safety and tolerability of tezepelumab compared with placebo
 
	
 
Subject incidence of adverse events (including serious adverse events)
 

Exploratory – Part A and Part B	

 
To estimate the long-term effect of tezepelumab on the efficacy measures of EASI, SCORAD, and Pruritus NRS
 
	
 
IGA 0/1 at week 24, week 36, and week 52
 
EASI 75 at week 24, week 36, and week 52
 
EASI 50/90 at week 24, week 36, and week 52
 
SCORAD at week 24, week 36, and week 52
 
Pruritus NRS at week 24, week 36, and week 52
 

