**Patients will be asked the following questions:**

**“On a scale of 0 to 10, with 0 being ‘no itch’ and 10 being the ‘worst itch imaginable’, how would you rate your itch during the previous 24 hours?”**

The mean weekly Pruritus NRS is calculated as the prorated average of the reported daily NRS within the week. For example, if there are 3 scores in a week, the prorated average = (score1 + score2 + score3)/3.

**For subjects who take rescue medication of TCS/TCI after day 29, their Pruritus NRS score will be ignored on and after the date of rescue medication.**

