#### **8.3.2 Missing Post-baseline Evaluation**

Refer to [Section 9.5.1.1](#) for handling of missing data for primary estimands defined in [Section 2.1](#).

**Secondary and exploratory endpoints will be included in descriptive summaries as observed without imputation for missing data. In analyses of secondary/exploratory endpoints involving statistical models detailed in [Section 9.5.2](#) and [Section 9.5.3](#), where endpoints cannot be derived due to missing IGA or EASI assessments, the missing binary endpoints (IGA 0/1, EASI50, EASI75,**

**EASI90) will be imputed using non-responder imputation (NRI). Missing binary endpoints that are not derived from IGA or EASI data (eg, Pruritus NRS  $\geq 2$ ) and missing continuous endpoints will not be imputed unless otherwise specified.**

Missing post-baseline safety data will not be imputed.

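### Week-16 SCORAD and Pruritus NRS: protocol and SAP disagree on missing data, SAP 2.1 and 5.4 disagree on rescue, and the day-29 cutoff differs between endpoints

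*Protocol*

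**What the plan says.** **Missing week 16.** Protocol 10.2.4 states, for the change-from-baseline secondary endpoints, that "subjects missing week 16 will have their last observation carried forward". Multiple imputation and a completers analysis are named only as possible sensitivity analyses. SAP 8.3.2 says "missing continuous endpoints will not be imputed unless otherwise specified". SAP 9.5.2 analyses both endpoints with an MMRM with AR(1) covariance and names no imputation step.

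**Rescue.** SAP 2.1 sets the strategy for the primary estimands: "use of TCS/TCI will be classed as a non-response". It then says "The secondary estimands are described in the same way as primary estimands except the endpoint attribute will change", and for SCORAD and Pruritus NRS it makes the summary measure a least-squares mean difference. SAP 5.4 has a separate rule. For subjects who "take rescue medication of TCS/TCI after day 29, their Pruritus NRS score will be ignored", scores are dropped from the rescue date onward. The SCORAD entry has the same rule.

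**Follow-up and timing of rescue.** Protocol 7.1.5 has subjects complete all visits and assessments "whether or not they complete study treatment or receive rescue treatment for AD". It also says "Rescue is not allowed in the first 4 weeks of Part A".

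**Cutoff.** In SAP 5.4 the IGA and EASI entries apply to rescue *from* day 29, as do the primary endpoints in SAP 5.5. The entries for SCORAD, Pruritus NRS, EQ-5D, POEM, PGI-S and DLQI apply to rescue *after* day 29.

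**The concern.** A reader of the study report needs to know what the SCORAD and itch differences estimate. The plan gives conflicting answers. The protocol describes a last-observation analysis. SAP 2.1 describes an estimand in which rescue is failure. The SAP's working rules produce a model-based estimate for subjects as if rescue had not been taken. If nothing changes, the MMRM result carries an estimand label that it does not match, and the departure from the protocol goes undeclared. Separately, a subject who starts TCS or TCI on day 29 may count as rescued for EASI and unrescued for SCORAD and itch within the same report.

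**Working it through.** The plan has no power or precision figure for SCORAD or Pruritus NRS to reproduce. The check sets the passages side by side.

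| Situation | Protocol 10.2.4 | SAP 2.1 | SAP 5.4, 8.3.2, 9.5.2 |
|---|---|---|---|
| Week 16 missing, no rescue | Last score carried forward | No rule for missing scores | No imputation; MMRM uses the earlier visits |
| Rescued, week-16 score recorded | Not triggered: nothing is missing | Non-response by inheritance; no score defined | Score ignored; MMRM |
| TCS/TCI started on day 29 | No rule | Follows the primary endpoints, which count from day 29 (5.5) | Scores ignored for IGA/EASI; kept for SCORAD and PROs if the rule is applied to the start date |

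**Row 1: protocol against SAP.** Both texts address the same event and prescribe different things. The visible entries in SAP section 10 are the added POEM and EQ-5D-3L objectives and the event-of-interest definition. The replacement of LOCF is not among them.

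**Row 2: SAP against SAP.** Non-response is a value of a binary endpoint. A least-squares mean difference needs a number for each subject, and 2.1 supplies none. Under 5.4 the post-rescue scores are treated as missing. Under missing at random, the MMRM then estimates the week-16 mean had TCS/TCI rescue not been taken. That is a hypothetical strategy, whereas the inherited one is composite.

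**Row 3: cutoff.** The SAP's target day is week × 7 + 1, so week 4 is 4 × 7 + 1 = day 29. Four weeks cover days 1 to 28, so day 29 is also the first day after the Part A ban on rescue. A start on that day is plausible. The two wordings differ for that start date only.

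**Can a size be given?** The documents state about 60 subjects per arm and 10% dropout, but no means, SDs or rescue rates for these endpoints. Two simulations with assumed SCORAD inputs compared discard-plus-MMRM with LOCF of the last pre-rescue score (differences are active minus placebo):

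- *Set 1.* Change −15 placebo and about −32 active, SD 18, correlation 0.7, rescue 29%/12% to 63%/35% (placebo/active), rescue-date score dropped. MMRM gives −14.3 to −10.7 and LOCF −17.2 to −15.8. MMRM minus LOCF is −14.3 − (−17.2) = +2.9, up to −10.7 − (−15.8) = +5.1, so the MMRM effect is smaller.
- *Set 2.* Change −18 and −32, residual SD 18, correlation 0.75, 10% dropout, rescue 28%/17% to 55%/40%, score prompting rescue kept. MMRM gives −13.9 to −14.0 and LOCF −13.3 to −11.8. MMRM minus LOCF is −13.9 − (−13.3) = −0.6, up to −14.0 − (−11.8) = −2.2, so the MMRM effect is larger.
- *Set 2 without rescue.* MMRM gives −13.9 and LOCF −13.4, a gap of 0.5 points against a standard error of about 3.4 at 60 per arm.

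The sign reverses with the assumptions. One difference between the sets is whether the score that prompted rescue is itself discarded. LOCF after discarding post-rescue scores is also a combination that no passage states. These runs therefore show only that no size or direction can be claimed.

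**The case against.** The strongest reply is that the SAP's operative rules agree with one another. Sections 5.4, 8.3.2 and 9.5.2 all say discard, do not impute, fit the MMRM, and protocol 10.3.2.2 leaves the details of the secondary analysis to the SAP. SAP 2.1 says that rescue is captured through the endpoint definition in 5.5, which is binary, and then changes the endpoint for SCORAD and NRS. It also summarises the primary estimand as response without rescue, which partly fits the discard rule. The endpoints are descriptive, with nominal p-values.

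Most of this stands. A programmer would probably follow 5.4 and 9.5.2, and the SAP may replace LOCF. What remains is that section 10 exists to declare such changes, and that 2.1 alters the endpoint and summary measure but never replaces the rescue strategy.

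Stronger readings are tempting and do not hold:

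- *Three incompatible rules for one event.* The LOCF sentence covers missing week-16 data and does not mention rescue. Rescued subjects keep attending, so their week-16 score is normally recorded.
- *All scores after day 29 are discarded.* Only scores from the date of TCS/TCI rescue are.
- *The plan shifts the SCORAD effect by a known amount, or in a known direction.* The documents give no inputs for this, and the illustrations disagree in sign.

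**Conclusion.** The point holds as two pairwise conflicts and one cutoff inconsistency. Protocol LOCF conflicts with the SAP's MMRM without imputation for a missing week 16, and the visible section 10 does not declare the change. The non-response strategy inherited in SAP 2.1 conflicts with the discard rule in 5.4, and non-response is undefined on a continuous scale. The day-29 boundary differs between IGA/EASI and the other endpoints; it matters only for rescue starting that day, and only if the rule is applied to the start date. These conclusions rest on the text alone. The effect on the treatment difference is not quantified because the documents do not allow it. The primary endpoints and their error control are unaffected. The correction is worth making before unblinding because it settles what the SCORAD and itch results can be said to estimate.

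**What to change.** 1. In SAP 2.1, state the rescue strategy for SCORAD and Pruritus NRS directly: the value had TCS/TCI rescue not been taken, which is what 5.4 and 9.5.2 implement. Do not let these endpoints inherit non-response. The handling of stopping investigational product can stay as it is.
2. Keep the MMRM as the main analysis and list the departure from protocol LOCF in SAP section 10.
3. Run the protocol's LOCF as a named sensitivity analysis, saying whether it is applied before or after post-rescue scores are removed.
4. In SAP 5.4, change after day 29 to from day 29 for SCORAD, Pruritus NRS, EQ-5D, POEM, PGI-S and DLQI.

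The cost is a few sentences and one extra table for each of the two endpoints. The downside is that the extra table may show a different estimate. No change to data collection or to subject management is involved.
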